13.4 Clinical Laboratory Evaluation

Laboratory values will be classified as normal, low, or high based on normal ranges supplied by the laboratory. Changes from baseline in abnormality status will be summarized using shift tables.

For quantitative laboratory measures (chemistry and hematology), observed values and changes from baseline will be summarized descriptively by visit.

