4.3 Exclusion Criteria

A subject who meets any of the following criteria will be excluded and considered ineligible for participation in the study:

1. Concurrent conditions:
 - a. Immunocompromised (e.g., lymphoma, acquired immunodeficiency syndrome) or medical history of positive human immunodeficiency virus antibody at Screening.
 - b. Chronic or acute systemic infection requiring treatment with antiparasitics, or antiprotozoals, within 4 weeks prior to the Baseline visit.
 - c. Chronic or acute systemic bacterial infection requiring treatment with systemic antibiotics within one week prior to the Baseline visit.
 - d. Chronic or acute superficial fungal infection requiring treatment with systemic antifungals within one week prior to the Baseline visit
 - e. Acute active bacterial, fungal, or viral (herpes simplex, herpes zoster, chicken pox) skin infection within one week prior to the Baseline visit; the condition should be completely resolved one week prior to Baseline Visit
 - f. Significant dermatologic or inflammatory condition other than AD that, in the Investigator's opinion, would make it difficult to interpret data or assessments during the study. For example, subjects with an active skin condition such as Kaposi's varicelliform eruption, scabies, molluscum contagiosum, impetigo, psoriasis, severe acne, connective tissue disorder, or Netherton's syndrome, or any other concurrent active disease.
 - g. Concurrent skin lesions in the treatment area or pruritus due to conditions other than AD that, in the opinion of the Investigator, would either interfere with study evaluations or affect the safety of the subject.
2. Screening alanine aminotransferase (ALT) or aspartate aminotransferase (AST) $\geq 2.0 \times$ the upper limit of normal (ULN).
3. Screening total bilirubin $> 1.5 \times$ ULN; total bilirubin $> 1.5 \times$ ULN is acceptable if bilirubin is fractionated and direct bilirubin $< 35\%$.

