4. Current or chronic history of liver disease, known hepatic or biliary abnormalities (with the exception of Gilbert's syndrome or asymptomatic gallstones), presence of hepatitis B surface antigen (HBsAg), or positive hepatitis C antibody test result, or presence of anti-hepatitis B core antigen (anti-HBc). Subjects having a negative HBsAg and a positive anti-HBc may enroll if they have a positive anti-hepatitis B surface antigen demonstrating natural immunity. Subjects with a history of hepatitis C virus infection who were medically cured and have an undetectable viral load are eligible to enroll. Subjects with a history of stable non-alcoholic fatty liver disease without evidence of active inflammation (elevated ALT/AST $\geq 2.0 \times$ ULN) or cirrhosis are eligible to enroll.

5. Current or a history of cancer within 5 years except for adequately treated skin basal cell carcinoma, cutaneous squamous cell carcinoma or carcinoma in situ of the cervix (surgical excision or electrodesiccation and curettage).
6. Subjects who would not be considered suitable for topical therapy (e.g., those with extensive disease involvement over a large BSA who would be candidates for systemic therapy).
7. Use of any prohibited medication or procedure within the indicated period before the Baseline visit.

NOTE: Prohibited concomitant medications, therapy, etc. during the defined period are as listed in the bullets below. If a subject requires any of these medications throughout the study period, he/she may be excluded from or discontinued from the study, at the discretion of the Investigator and Medical Monitor.

- a. From 4 months prior to Baseline until the completion of the Follow-up visit or study discontinuation:
 - DUPIXENT® (dupilumab) injection.
 - Any monoclonal antibody product that becomes approved for AD during the course of the trial.
- b. From 28 days prior to Baseline until the completion of the Follow-up visit or discontinuation:
 - Oral, injectable, and suppository preparations of corticosteroids. Eye drops and nasal preparations are allowed. Inhaled preparations are allowed when used for a stable condition and stable dose for \geq 28 days before Screening and are continued at the same dose throughout the study.
 - Oral preparations and injections of immunosuppressants (cyclosporine, methotrexate, azathioprine, tacrolimus, Janus kinase inhibitors, etc.).

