8.2 Classification of Adverse Events

8.2.1 Assigning Severity Rating for Adverse Events

8.2.1.1 Criteria for Determining Adverse Event Severity

The Investigator will make an assessment of the severity of each AE and SAE according to the National Cancer Institute CTCAE, v. 5.0, 2017. For terms not specified with the CTCAE, the criteria in Table 5 should be used to determine the grade severity.

Table 5: Criteria for Determining the Grade/Severity of Adverse Event Terms Not Specified by the National Cancer Institute CTCAE

Grade	Criteria
1	Mild; asymptomatic or mild symptoms, clinical or diagnostic observations only; intervention not indicated
2	Moderate; minimal, local, or noninvasive intervention indicated; limiting age-appropriate instrumental activities of daily living ^a
3	Severe or medically significant but not immediately life-threatening; hospitalization or prolongation of hospitalization indicated; disabling; limiting self-care activities of daily living ^b
4	Life threatening consequences; urgent intervention indicated
5	Death related to adverse event

a. Instrumental activities of daily living refer to preparing meals, shopping for groceries or clothes, using the telephone, managing money, etc.

b. Self-care activities of daily living refer to bathing, dressing and undressing, feeding self, using the toilet, taking medications, and not bedridden.

CTCAE = Common Terminology Criteria for Adverse Events.

AE severity should be recorded in the appropriate section of the AE CRF and in the subject's source documents.

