6. GENERAL ANALYSIS CONSIDERATIONS

The statistical analyses will be reported using summary tables, listings, and figures (TLFs). The International Council for Harmonisation (ICH) numbering convention will be used for all TLFs.

All study data will be summarized by age group (2-6 years old, 7-11 years old, and 12-17 years old) and overall using descriptive statistics.

Categorical endpoints will be summarized by presenting counts and percentages of subjects in corresponding categories. All possible categories as defined in the CRF should be populated, even if they have zero counts. Percentages for missing values are omitted and do not account for the percent calculation of other categories. Percentages are based on the total category count excluding the missing category if not otherwise mentioned. In certain tables (e.g., AEs), the total number of subjects is used as denominator. Footnotes will specify the percent basis in those cases.

Continuous endpoints will be summarized by presenting the number of observations, means, standard deviations, medians, minimums, and maximums.

Individual subject data obtained from the eCRFs, external vendors (e.g., central clinical laboratory data, PK data) and any derived data will be presented by subject in data listings.

The analyses described in this plan are considered a priori, in that they have been defined prior to database lock. Any analyses performed after database lock will be considered post-hoc and exploratory. Post-hoc analyses will be labeled as such on the output and identified in the CSR.

All TLFs will be programmed using Statistical Analysis System® (SAS®) software Version 9.4 or higher. Tables, listings, and figures will be presented in rich text format (RTF).

The process for SAS program validation and quality control (QC) for programs and outputs is documented in the Synteract working instruction “SAS programming quality control.” Study-specific QC requirements can be found in Appendix B: SAS programming QC requirements.

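### The low/normal/high laboratory shift table in SAP 13.4 cannot register a further rise in a child already above the ULN, and no planned table bands ALT, AST or bilirubin by multiple of ULN

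*SAP*

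**What the plan says.** **Laboratory tables.** SAP 13.4 specifies: "Laboratory values will be classified as normal, low, or high based on normal ranges supplied by the laboratory". It continues: "Changes from baseline in abnormality status will be summarized using shift tables". Protocol 10.4.2 sets the same rule. No other categorical laboratory analysis is planned. For chemistry and hematology, SAP 13.4 adds that "observed values and changes from baseline will be summarized descriptively by visit". SAP section 6 fixes the statistics: "Continuous endpoints will be summarized by presenting the number of observations, means, standard deviations, medians, minimums, and maximums". It also provides that data from "external vendors (e.g., central clinical laboratory data, PK data) and any derived data will be presented by subject in data listings".

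**Eligibility (Protocol 4.3).** ALT or AST excludes a child only at 2.0 x ULN or more. Total bilirubin above 1.5 x ULN "is acceptable if bilirubin is fractionated and direct bilirubin" is below 35%; no upper limit is given. "Subjects with a history of stable non-alcoholic fatty liver disease without evidence of active inflammation" may also enter, subject to the same ALT/AST limit and absence of cirrhosis.

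**Adverse events.** An abnormal laboratory result is an adverse event if the investigator judges it clinically significant (Protocol 8.1.1). Severity is then graded "according to the National Cancer Institute CTCAE, v. 5.0, 2017", and SAP 13.2 tabulates the maximum grade.

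**Visit assignment.** SAP 7 maps early-termination and unscheduled assessments to windows (Week 1 up to Day 18, Week 4 from Day 19). Where several fall in one window, it keeps the one closest to the target day.

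**The concern.** A shift table shows which children moved from acceptable to abnormal values. With one undivided high category, a child who enters above the ULN has no worse cell to move to. The eligibility criteria knowingly admit such children for ALT, AST and bilirubin, so the situation is foreseeable. The same coarseness affects children who start normal: a value just over the limit and a value many times the limit share one cell.

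Change from baseline in laboratory values is among the primary endpoints, and the study's purpose is to look for systemic effects under maximal use. A reader of the report would want to know how many children reached a given multiple of the ULN, and from what starting level. No planned table answers that. The next section of the same SAP, 13.5, does this for blood pressure: it defines abnormal and markedly abnormal changes, and tabulates and lists the marked ones.

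**Working it through.** The plan states no figure to reproduce: the study is descriptive and its sample size rests on feasibility (SAP 5). The check has four parts.

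**1. Apply the rule.** Classify as high if the value exceeds 1 x ULN. The ALT/AST values are illustrations, in multiples of ULN; every baseline shown is below the 2.0 x ULN exclusion limit.

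| Baseline | Post-dose | Shift cell | Change |
|---|---|---|---|
| 1.05 | 1.99 | high to high | +0.94 |
| 1.5 | 3.1 | high to high | +1.60 |
| 1.99 | 8.0 | high to high | +6.01 |
| 0.9 | 1.05 | normal to high | +0.15 |

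The smallest change is the only one that counts as a shift.

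**2. See what the change-from-baseline summary shows.** Suppose one child goes from 1.99 to 8.0 x ULN and all others are unchanged. The mean change is 6.01/n:
- n = 36 (overall): 6.01/36 = 0.17 x ULN
- n = 12 (planned cohort): 6.01/12 = 0.50 x ULN
- n = 10 (minimum cohort): 6.01/10 = 0.60 x ULN

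The median change is 0 and the maximum is +6.01 x ULN. The case is therefore visible in the maximum, diluted in the mean and absent from the median. The SAP does not ask for this summary in ULN multiples, and a maximum does not say how many children crossed a threshold.

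**3. Check whether a peak survives the visit rules.** Protocol 7 schedules safety blood tests at Screening and Day 28, at early termination, and at follow-up if needed. Protocol 7.8 allows unscheduled draws. An unscheduled sample on Day 22 falls in the Week 4 window, 6 days from target. A scheduled Day 28 sample is 0 days from target and is the one analyzed. A Day 22 peak would then be absent from the by-visit tables, though present in the listing. An early-termination sample up to Day 18 is labelled Week 1, so a table confined to Week 4 would omit it.

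**4. Estimate how many children could be affected.** The documents give no prevalence p of values above the ULN. Assume p per test, with p = 2.5% if the laboratory range is a central 95% interval.
- Baseline classifications for the three tests: 36 x 3 = 108; expected high at p = 2.5%: 108 x 0.025 = 2.7.
- Chance that at least one of 36 children starts high on a given test, 1 - (1 - p)^36: 30% at p = 1%, 60% at 2.5%, 84% at 5%.
- Normal-to-high shifts by chance alone, at p = 2.5% and with bivariate normal values: the probability per classification is 0.0238 at test-retest correlation 0 and 0.0140 at correlation 0.8. Over 108 classifications that is 108 x 0.0238 = 2.6 and 108 x 0.0140 = 1.5.

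**The case against.** A reader might infer that worsening liver tests are reported as unchanged, or that the primary laboratory endpoint is blind to them. The documents do not support that. The endpoint is change from baseline, and the second paragraph of SAP 13.4 summarizes it directly, with a maximum measured against each child's own baseline. All laboratory data are listed by subject, which for about 36 children can be read case by case. Clinically significant abnormal values are to be repeated (Protocol 6.3.4) and become CTCAE-graded adverse events. The ceiling is a property of the shift table only.

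A reader might also size the problem across all 30 chemistry and hematology analytes in Protocol Table 4, which gives 36 x 30 x 0.025 = 27 high baseline classifications. That is ten times too many for this point: the eligibility argument concerns three tests, hence 2.7. Nor do the documents say that children admitted with raised values have less hepatic reserve.

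It is also fair to say that the study is single-arm and descriptive, with no formal safety comparison, so no error rate or decision rule changes.

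These objections limit the point without removing it. The adverse-event route depends on investigator judgment. The change summary is not in ULN multiples. The by-visit tables can drop an unscheduled peak. A count of children by ULN band remains absent.

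**Conclusion.** The point holds in a narrow form. The three-level shift table cannot show upward worsening in a child who starts above the ULN, and the protocol admits such children for ALT, AST and bilirubin. Other planned outputs can reveal an individual case. None counts children by multiple of ULN or uses the worst post-baseline value.

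The ceiling follows from the text and needs no assumption. The number of children affected cannot be determined from the documents. The figures of 2.7 high baseline classifications and about 60% for at least one child on a given test rest on an assumed 2.5% prevalence; the probability runs from 30% to 84% for 1% to 5%. The chance-shift figures of 1.5 to 2.6 also assume bivariate normal values. Severity: a minor reporting improvement.

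**What to change.** In SAP 13.4, keep the existing shift tables and add the following for ALT, AST and total bilirubin:

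- **Table.** A shift from baseline to worst post-baseline value by ULN-multiple band, including unscheduled, early-termination and follow-up samples.
- **Bands.** Start from the protocol's own cut-points: 1 and 2.0 x ULN for ALT and AST, 1 and 1.5 x ULN for bilirubin. The sponsor should prespecify higher bands for all three tests so that no admitted child starts in the top band. Stopping bilirubin at above 1.5 x ULN would rebuild the ceiling for the children admitted above it. Because bilirubin entry has no stated upper limit, an alternative is to add a measure of increase relative to the child's own baseline.
- **Reporting.** Count and list every child who moves up a band.

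This uses data already collected and changes no sample size, eligibility criterion or visit. The cost is SAP wording and a few extra tables, with possibly more visible worsenings to explain.

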
 Incidence, frequency, and duration of treatment emergent adverse events (TEAEs) and serious adverse events (SAEs) Change from Baseline in laboratory values Change from baseline in vital signs Mean Investigator-assessed LTS scores by visit (overall and sensitive areas) Tapinarof plasma PK parameters on Day 1, if data permit, including: 
 area under the plasma concentration versus time curve from time zero to the last quantifiable concentration (AUC_{0-last}) maximum plasma concentration (C_{max}) time to maximum plasma concentration (t_{max}) time of last quantifiable concentration (t_{last}) Tapinarof plasma concentration on Day 28 	
Secondary:	

 Change in vIGA-AD™ score from Baseline at each study visit Proportion of subjects who have a vIGA-AD™ score of clear or almost clear (0 or 1) at each study visit Proportion of subjects with \geq50% improvement in EASI score from Baseline at each study visit Proportion of subjects with \geq75% improvement in EASI score from Baseline at each study visit Proportion of subjects with \geq90% improvement in EASI score from Baseline at each study visit Mean change and percent change in EASI score from Baseline at each study visit Mean change and percent change in %BSA affected from Baseline at each study visit Mean change and percent change in BSA x vIGA-AD™ values from Baseline at each study visit Proportion of subjects with a Baseline PP-NRS score \geq 4 who achieve \geq 4-point reduction in the PP NRS from Baseline at each study visit Proportion of subjects \geq 12 years old with a Baseline PP-NRS score \geq 4 who achieve a \geq 4-point reduction in PP-NRS score from Baseline at each study visit Proportion of subjects 2 to $<$ 12 years old with a Baseline PP-NRS score \geq 4 who achieve a \geq 4-point reduction in PP-NRS score from Baseline at each study visit Mean change in PP-NRS score from Baseline to Day 28 at each study visit by age group 	
Statistical Methods:	
Safety Analyses:	

 Analyses of the safety endpoints will be based upon the Safety population, which is defined as all enrolled subjects who receive at least 1 application of study drug. 	

- AEs will be summarized as incidence rates of any AEs, TEAEs, AEs of special interest, treatment-related TEAEs, TEAEs leading to study drug discontinuation, TEAEs leading to study discontinuation, and SAEs.

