- c. Physical examination will include height and weight, (BMI will be calculated in the CRF); a brief physical examination will be performed at other visits.
- d. Medical history will include month and year of AD diagnosis. As part of the subject's medical history, all systemic (oral and injectable) medications used by the subject for treatment of AD prior to 30 days before the Screening visit will be collected.
- e. Record any changes to medical history and document changes in source and EDC.
- f. Serum pregnancy test to be performed at the Screening visit only and urine pregnancy test to be performed at subsequent clinic visits when pregnancy testing is being performed.
- g. Urine pregnancy test to be performed before dosing.
- h. Clinical laboratory assessments include serum chemistry and liver chemistry tests, and hematology.
- i. If needed for ongoing AE or laboratory abnormality from previous visit.
- j. Vital signs will include systolic and diastolic blood pressure, pulse rate, and body temperature and should be measured after the subject is seated for at least 5 minutes. Vital signs will be measured before blood collection for clinical laboratory assessments and PK analysis.
- k. Site personnel will weigh the tubes to be dispensed and will record the weight of all tubes dispensed at each visit in the drug accountability logs. Site personnel will weigh the returned tubes (used and unused) and record the weight in the drug accountability logs. If a tube has been lost, discarded, or forgotten by the subject, then the site personnel will make a notation of this on the drug accountability logs.
- l. Subjects and/or caregivers will be instructed to apply study drug once daily at the approximate same time each day, based on subject and/or caregiver(s) preference.
- m. At all clinic visits, study drug will be applied after all safety and efficacy assessments have been conducted.
- n. The blood sample collected at Screening will serve as the pre-dose plasma concentration. PK sampling will occur on Day 1 at 1, 3, and 5 hours post-dose. A single PK sample will be collected on Day 28.
- o. The vIGA-AD™ assessment should be performed before the %BSA and EASI assessments.
- p. The subject's scalp should be excluded from the %BSA and EASI calculation.
- q. The LTS assessment should be conducted pre-dose.
- r. PP-NRS daily itch diaries will be dispensed at Day 1 (Baseline) and Day 8 and collected on Day 28.

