7.6 Visit 5; Follow-Up (Day 35 ±3 Days)

Subjects who do not enroll in the open-label long-term safety study will return to the study site 7-10 days after Day 28 to complete follow-up assessments as follows:

- Brief physical examination
- If needed, blood sample collection for clinical laboratory tests
- If needed, urinalysis
- Vital signs measurement
- AE recording
- Concomitant medication recording
- vIGA-AD™ score (excluding subject's scalp)
- %BSA affected calculation (excluding subject's scalp)
- EASI (excluding subject's scalp)

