5. DETERMINATION OF SAMPLE SIZE

Approximately 36 subjects ages 2 to 17 years old will be enrolled in the study with approximately 12 subjects, and a minimum of 10 subjects, enrolled into each of the three following age cohorts: 2-6 years old, 7-11 years old, 12-17 years old.

There is no formal statistical hypothesis planned and the sample size is mainly based on feasibility and an estimated number of subjects needed to address the objectives of the study.

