7. NOTATION OF TREATMENT GROUPS AND VISITS

Notation of treatment groups

The following notation of **treatment groups** will be used throughout the report:

Full Notation (as used in the study protocol)	Notation Used Throughout All Tables, Listings, and Figures
Tapinarof Cream 1%	Tapinarof Cream 1%

Visit terminology

Visit	Notation Used Throughout All Tables, Listings, and Figures
Screening, Days -30 through Day -1, Visit V1	Screening
Baseline, Day 1, Visit V2	Baseline
Week 1, Day 8, Visit V3	Week 1
Week 4, Day 28, Visit V4 (End of Treatment)	Week 4
Week 5, Day 35, Visit V5 (End of Study/Follow-up)	Week 5

Note: A phone call to assess AEs and concomitant medications, to review study drug application procedures, and to confirm subject's continued participation in the study will occur on Week 2 (Day 15).

Analysis visits

Study days are measured from date of first dose of study medication. Study days corresponding to measurements are calculated as:

- Assessment date – date of first dose + 1 if assessment date is on or after the date of first exposure of treatment.
- Assessment date – date of first dose if assessment date is before the date of first exposure of treatment.

All efficacy, PK, and safety endpoints will be analyzed according to the nominal visits (i.e., actual visit) except for assessments collected on early termination and unscheduled visits. Early termination and unscheduled visits will be re-numbered to an analysis visit based on their windowed visits defined by actual study day. If more than one visit occurs within a single visit window, then the analysis will take the one closest to the target day. If the 2 visits are equidistant from the target day, the visit with later date and time will be used.

The following analysis visit windows will apply to early termination and unscheduled visits:

Analysis Visit	Target Day	Analysis Visit Window
Baseline	1	1
Week 1	8	Post first dose to Day 18
Week 4 (End of Treatment)	28	Day 19 – Maximum (last day of treatment + 3 days, Day 31)

Analysis Visit	Target Day	Analysis Visit Window
Week 5 (End of Study)	35	>Maximum (last day of treatment + 3 days, Day 31)

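### By-visit laboratory summaries would create Week 1 and Week 5 rows built from non-scheduled or for-cause samples that cannot be compared with Week 4

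*SAP*

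**What the plan says.** "Change from Baseline in laboratory values" is one of the primary endpoints (protocol synopsis and Section 2).

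**Collection.** Protocol Table 1 and Sections 7.1 to 7.8 place laboratory samples as follows:
- Screening: routine.
- Day 1 and Visit 3 (Day 8): none.
- Day 28: routine for everyone still in the study.
- Day 35 Follow-up: conditional. Table 1 note i reads "If needed for ongoing AE or laboratory abnormality from previous visit", and Section 7.6 reads "If needed, blood sample collection for clinical laboratory tests". Only children who do not enter the long-term study attend.
- Early termination: routine, whatever the reason for leaving.
- Unscheduled visits: as needed.

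**Analysis.** SAP 13.4 states: "For quantitative laboratory measures (chemistry and hematology), observed values and changes from baseline will be summarized descriptively by visit". It also plans shift tables of abnormality status, without saying which post-baseline value they use or whether they are by visit. SAP 7 states: "Early termination and unscheduled visits will be re-numbered to an analysis visit based on their windowed visits defined by actual study day". Its windows run from after the first dose to Day 18 (Week 1), from Day 19 to the later of Day 31 and three days after the last treatment day (Week 4), and beyond that (Week 5). Where two visits share a window, the one nearer the target day is used. On denominators, SAP 6 states: "Percentages are based on the total category count excluding the missing category if not otherwise mentioned".

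**The concern.** The SAP treats every analysis visit as a laboratory visit, but only Week 4 is one for the whole cohort. Two kinds of unrepresentative row follow. Week 1 has no scheduled draw, so whatever appears there comes from children who left early or had an extra visit. Week 5 has a draw only when something prompted it. Children not tested by design leave the denominator as if they were ordinary missing data.

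The study has no control arm, and results are shown in age cohorts of about 12. A reader comparing a Week 5 row with Week 4 could take a few retested children for a laboratory signal that appears or persists in the cohort.

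There is a loss in the other direction too. The closest-to-target rule keeps one visit per window, so an abnormal unscheduled value can disappear from the summaries when a visit nearer the target day exists.

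**Working it through.** The documents give no figure to reproduce here: the sample size rests on feasibility and no hypothesis is tested. The check has two parts.

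**1. Tracing samples through the SAP 7 windows**

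| Sample | Analysis visit |
|---|---|
| Early termination or unscheduled, Days 3, 10, 14, 18 | Week 1 |
| Early termination or unscheduled, Days 19, 25 | Week 4 |
| Unscheduled Day 31, last dose Day 27 (limit = max(27 + 3, 31) = 31) | Week 4 |
| Unscheduled Days 32, 35, last dose Day 27 | Week 5 |
| Scheduled Day 28 | Week 4 |
| Conditional Day 35 | Week 5 |

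No scheduled laboratory sample reaches Week 1. Week 5 receives the conditional Day 35 draws plus late unscheduled samples. The one routine route into Week 5 is a Day 28 visit made up after Day 31 with treatment already stopped, hence almost entirely for-cause rather than wholly so.

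*How often a Week 1 row would exist.* Assume 3-15% of 36 children terminate by Day 18 (the documents give no rate). Expected n = 36 × 0.03 = 1.1 to 36 × 0.15 = 5.4. The chance of at least one is 1 − 0.97^36 = 0.67 to 1 − 0.85^36 = 0.997. This assumes that the tie rule works per assessment. If it works per visit, a Day 8 visit without laboratory samples would displace a sample from Days 9-18. The SAP does not say which.

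*The tie rule at Week 4.* If an unscheduled Day 22 value is high and the scheduled Day 28 value is normal, Day 28 is nearer the target and the Day 22 value drops out of the summary.

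**2. Size of the Week 5 selection, if shift tables are by visit**

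Assumptions, none from the documents: no drug effect; log-scale SD 0.35 between and 0.25 within child; upper limit at the 97.5th percentile, so 2.5% of all children are high at any visit.

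Correlation between two visits = 0.35² / (0.35² + 0.25²) = 0.1225 / 0.185 = 0.66. For a bivariate normal with this correlation, P(high at Week 5 | high at Week 4) = 0.297.

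*Analyte that triggered the retest.* The Week 5 row shows about 30% high, and 0.297 / 0.025 = 11.9 times the 2.5% expected. If only that analyte is redrawn, each child has probability 0.025 × (1 − rollover) of a Week 5 value:

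| Rollover | P(row exists) = 1 − (1 − q)^36 | Mean n when it exists = 36q / P |
|---|---|---|
| 50% (q = 0.0125) | 0.36 | 1.24 |
| 75% (q = 0.00625) | 0.20 | 1.11 |
| 90% (q = 0.0025) | 0.09 | 1.04 |

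*Whole panel redrawn.* Table 1 note h describes the laboratory draw as a chemistry, liver and hematology panel, so most redrawn analytes were not the trigger. Take 20 independent analytes and redraw all if any is high at Week 4:
- P(any high) = 1 − 0.975^20 = 0.397.
- P(a given analyte is high at Week 5 | redraw) = [0.025 × 0.297 + 0.025 × 0.703 × (1 − 0.975^19)] / 0.397 = (0.00743 + 0.00671) / 0.397 = 3.6%.

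With assumed correlation between analytes of 0.3 or 0.6, simulation gives about 5.4% and 8.5%. With 30 analytes the range is 3.1-7.8%. A panel redraw also makes the row larger: 36 × 0.5 × 0.397 = 7.1 children at 50% rollover and 36 × 0.1 × 0.397 = 1.4 at 90%, still a minority of the 36.

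*Mean change.* Under no effect, Baseline and Week 5 are equally correlated with the Week 4 value that triggered the retest, so their difference has expectation zero. The observed Week 5 level is raised for the trigger analyte (geometric mean about 1.95 times that of all children), but its change from baseline is not biased.

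**The case against.** A reader might infer that this primary endpoint will report abnormality rates for children chosen because something was wrong, inflated about twelve-fold. The documents do not support that.

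- The endpoint is change from baseline, and SAP 13.4 applies its by-visit wording to observed values and changes. By-visit shift tables are suggested by the synopsis wording and by SAP 7, but neither SAP 13.4 nor protocol 10.4.2 states them.
- Early-termination samples are taken whatever the reason for leaving, and protocol 4.6 allows withdrawal at the subject's own request or for administrative reasons. Unscheduled visits include make-up visits and drug dispensation. Week 1 is therefore a selected group, but not necessarily an abnormal one.
- The twelve-fold figure holds only for the analyte that triggered the retest. A redrawn panel gives about 1.2 to 3.4 times the expected rate (3.1 / 2.5 to 8.5 / 2.5), and draws prompted by an unrelated adverse event would dilute it further.
- Misreading is partly guarded against. Continuous summaries show n, all safety data are listed by subject, and clinically significant abnormalities are also adverse events.

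All four points stand as limits on the claim. None removes the mechanism: nothing in the SAP stops the rows from being produced, and a visible n does not tell the reader why those children were tested. SAP 13.3 does stop the local tolerability frequencies at Week 4; the laboratory section has no such limit.

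**Conclusion.** The point holds as a fault of presentation and interpretation. Following the stated rules, any Week 1 laboratory row contains only early-termination or unscheduled samples, and any Week 5 row is almost entirely for-cause. Neither describes the cohort or can be compared with Week 4. This follows from the schedule and the windows and needs no numerical assumption.

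The inflation of abnormality percentages is conditional. It arises only if shift tables are by visit, and under the assumed no-effect model it is about 30% high for the triggering analyte or about 3-9% across a redrawn panel, against 2.5%. The SDs, the rollover rates and the correlations between analytes are all assumed.

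The laboratory endpoint as a whole is not compromised. Week 4 is scheduled for every continuing child and carries the main result, although early-termination samples from Day 19 onward also enter it. Separately, the closest-to-target rule can remove an abnormal unscheduled value from the summaries, and no planned table is specified to bring it back.

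**What to change.** In SAP 13.4:

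1. Limit by-visit laboratory summaries, and any visit-specific shift tables, to Baseline and Week 4/End of Treatment. State that laboratory samples are not assigned to Week 1 or Week 5.
2. List Follow-up results, and early-termination and unscheduled results outside the Week 4 window, separately and labelled as conditional or non-scheduled.
3. Add one shift table from baseline to the worst post-baseline value, using all post-dose samples, scheduled or not. The denominator is all treated children with any post-baseline value. Each child then counts once, and an abnormal unscheduled value cannot be lost to the window rule.

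The cost is SAP wording and one extra table, with no new data. The downside is that there are no separate Week 1 or Week 5 laboratory rows; those values appear in the listings and the worst-value table.
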